- Primary progressive, secondary progressive or progressive relapsing MS
- Patients known to have a history of recent drug or alcohol abuse
- Any severe disease other than MS compromising organ function, meaning: history of, or abnormal laboratory results indicative of any significant cardiac, endocrinologic, hematologic, hepatic, immunologic, metabolic, urologic, pulmonary, gastrointestinal, dermatologic, renal and/or other major disease, that in the opinion of the investigators, would preclude the administration of PLP10 for 30 months.
- History of severe allergic or anaphylactic reactions or known specific nutritional hypersensitivity.

Note

During "on intervention treatment" the patients (depending on their pathological status) will be treated according to the normal international guidelines. A thorough record of treatment (or change of treatments) for each patient will be kept. If a patient changes therapy to immunosuppressant or monoclonal antibody or any other treatment on physicians' decision then he/she will be considered as a drop-out; but continue to be medically followed for the intention to treat analyses purposes.

If a clinical documented relapse is reported during "normalization" period the entry baseline EDSS for that patient will be reported as the EDSS score documented at least 4 weeks after the last relapse during this period.

"Normalization period" will be a 6 months period between enrolment and entry baseline (the first 6 months of the trial that patients will be on the intervention treatment for only normalization purposes). For the result analyses this 6 month period will be considered as a period before entry baseline for all four treatment arms.

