This is an ITT study with a proof-of-concept purpose. The main question that has to be answered is primarily the ability of the interventions to reduce the annual relapses rate and secondly the disability accumulation when used in RRMS patients and how safe it is vs. placebo. All patients who prematurely discontinue the study drug will be encouraged to continue in the study and follow-up until the end of the planned treatment period, regardless of the treatments received. The data collected will be included for ITT analyses. The main analysis of ARR will include all confirmed (associated with new or worsening of pre-existing neurological signs, increase of at list 0.5 score on EDSS) relapses during the study, including relapses reported after study drug discontinuation. The lost to follow missing data will be handled by an appropriate statistical

method and included in the intention to treat analysis (ITT). The overall key analysis should be based on per-protocol (excluding all protocol violations) supported by the ITT analyses.

Other:

An independent Data Monitoring Committee (DMC) will monitor and review all clinical trial data on a regular basis (by the funder).

Investigators adherence will be also monitored by DMC through CRF follow up.

Duration of Study per Patient

The clinical study period is approximately 43 months total, including a screening period up to 1 month, a 6 month normalization, 24 months treatment period and 12 months extended follow up period, after completion. The actual research period is for a total of 30 months including 6 months normalization and 24 months treatment periods.

Methods

The whole procedure follows the clinical trial guidelines as required by the USA Food and Drug Administration (FDA), European Medicines Agency (EMA) and according to the standards of the International Conference of Harmonization (ICH). The Clinical study is in agreement with the rules of Good Clinical Practice (GCP).

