The key secondary endpoint is the **time to confirmed disability progression** defined as an increase of 1.0 on the EDSS from a baseline score, confirmed after 6 months, with an absence of an ongoing relapse at the time of assessment (progression cannot be confirmed during a relapse) and with no documented relapse during the 6-months period needed for the confirmation. The final EDSS score will also be confirmed 6 months after the end of the study.

Relapses should be treated with methylprednisolone at a dose of 1g intravenously per day, for three consecutive days followed by prednisolone by mouth at a dose of 1mg/kg of weight per day on a tapering scheme for three weeks.

Hematological (full blood count) and Biochemical analyses should be performed at enrolment, baseline, 12 months and 24months and at the end of the extended period; performed at accredited laboratory.

Blood should be collected from all randomized patients at the time of enrolment and at every scheduled clinical assessment and during relapses. Blood tubes should be appropriately labelled including date, patients' code, number of scheduled assessment, for every blood handling step. A portion of 2 ml total blood volume per patient (in anticoagulant solution) should be drawn and stored refrigerated (4°C) for the lipid extraction procedure (from red blood cells) within 24 hrs according to standard protocol.

Sample Size Estimation

Power calculations could not be done before the study because of the lack of information from previous studies on potential effect sizes. Based on the population size of our country and the centre of reference (CING) we believe that we will probably be able to enroll enough patients for this proof-of-concept study. The scientific knowledge/background of the agents used, novelty of the assessed interventions and the study-protocol design/set-up will be contributing to valuable information. Hopefully the "eligible" final enrolled sample size will be enough to collect quality data able to answer the addressed proof-of-concept questioned - efficacy indication. There is no any matter of ethical conflicts since all interventions will be used as adjuvant. Sample size will strictly be based on this subjects' availability parameter.

Brief Statistical Methods

The study will be considered successful if there is a significant difference between the treatments for either of the two endpoints.

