Baseline characteristics will be compared across all intervention groups by ANOVA or Kruskal-Wallis rank test for continuous variables and by an exact chi-squared test for categorical variables, as appropriate.

Each test will be performed with a significance level of 0.05 (P-values will be two-tailed).

Primary Endpoint

Annualized Relapse Rate (ARR):

A Poisson regression/ negative Binomial analysis will be used to analyze this endpoint. The analysis will allow for likely overdispersion due to within-subject correlations by basing standard errors on the empirical estimator of the parameter covariance matrix. The fixed factors in the model will include treatment and relevant pre-specified covariates.

The relapse rate will be calculated as the total number of relapses divided by the total number of patient-years followed for each treatment group. ARR differences will also be calculated among all comparable parameters and reported as percent difference (relative reduction).

Secondary Endpoint

Time to Confirmed Disability Progression:

For the secondary end-point outcome, the time to disability progression, Kaplan–Meier curves will be constructed. A Long-rank and Cox proportional-hazards regression model will be used to analyze this endpoint. The fixed factors in the model will include treatment and relevant prespecified covariates . Additional baseline characteristics will be considered for inclusion in secondary models.

If the usual normality assumptions are not met, the endpoints will then be analyzed by either Poisson regression, using a model similar to the one to be used for the ARR, Wilcoxon Rank-Sum tests, or proportional odds logistic regression models, depending on the nature of the endpoints and whether covariates will be included in the model.

Safety

All treatment emergent signs and symptoms (those that initially occur after taking the first dose of study medication, or those that worsen after taking the first dose of study medication) will be summarized and tabulated according to their severity (mild, moderate, or severe) and relationship (definitely not related, or related) to study medication. The rates will be compared between each group and placebo using Fisher's Exact test.

Missing Data

Missing data of the lost to follow patients will be imputed by use of the last-observation-carried-forward (LOCF) approach.

We thank every and each one of you, for your total cooperation.

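### The protocol calls itself ITT but makes per-protocol the key analysis, so the deciding comparison can rest on a set selected after randomisation, and the success rule names neither population

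*Protocol*

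**What the plan says.** All three statements on the analysis population stand in one paragraph of the protocol's Missing Data Handling section. It opens with "This is an ITT study with a proof-of-concept purpose". It then says that the main analysis of the annualised relapse rate covers all confirmed relapses, "including relapses reported after study drug discontinuation". It closes with "The overall key analysis should be based on per-protocol (excluding all protocol violations) supported by the ITT analyses". No other section reverses that order.

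Three other places bear on the point:

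- **Note, after the exclusion criteria.** If the physician changes a patient to an immunosuppressant, a monoclonal antibody or any other treatment, "he/she will be considered as a drop-out; but continue to be medically followed for the intention to treat analyses purposes".
- **Drop Outs.** Drop-outs are followed in the same way as everyone else, so that ITT analyses are possible.
- **Brief Statistical Methods.** "The study will be considered successful if there is a significant difference between the treatments for either of the two endpoints". Tests are two-sided at 0.05. No population is named.

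**The concern.** The word superiority does not appear, but the design is one of superiority. The question is "primarily the ability of the interventions to reduce the annual relapses rate" against placebo, success is a significant difference, and there is no non-inferiority or equivalence margin. In such a trial the conclusion should rest on the groups as randomised. A set that excludes all violators is defined by what happens after randomisation. If leaving the set is related to relapses, the key comparison of relapse rates is selected on its own outcome.

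The protocol also uses two labels of similar rank, *main* and *key*, for analyses of different populations, and a success rule that is silent on which of them counts. If the two disagree, the protocol does not settle whether the trial succeeded.

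**Working it through.** **1. The statements side by side.** Calling the trial ITT and counting relapses after discontinuation is one coherent position. Basing the key analysis on per-protocol, with ITT in support, is a second position. Under Study Procedures and End Points the product is to be taken every day for 30 months. A patient who stops has therefore departed from the protocol, and would be expected to leave a set without violations. The first position counts that patient's later relapses; the second would not.

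**2. Can exclusion depend on relapses?** The Note makes a physician-decided change of therapy a drop-out and keeps the follow-up for ITT purposes. This implies, but does not state, that such patients leave the per-protocol set. If they do, and if some changes follow relapses, exclusion depends on the primary outcome.

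**3. Size.** The protocol gives no sample size, power or expected relapse rate, so it has no figure to reproduce. All inputs below are assumptions except the 24-month on-treatment period:

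- annual rate 0.7 on placebo, so mean m = 2 × 0.7 = 1.4 relapses per patient;
- gamma-Poisson counts with shape k = 1.5;
- exclusion probability 0.10 for everyone, plus an extra e for patients with two or more relapses.

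Formulas, with Y the relapse count:

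- P0 = (k/(k+m))^k
- P1 = k × m/(k+m) × P0
- Q = P(Y≥2) = 1 − P0 − P1
- S = the part of the mean due to patients with Y≥2 = m − P1
- per-protocol mean M = [0.90 × P1 + (0.90 − e) × S] / [0.90 × (P0 + P1) + (0.90 − e) × Q]

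For m = 1.4: P0 = 0.3720, P1 = 0.2694, Q = 0.3586, S = 1.1306.

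- e = 0.10: M = 1.1469/0.8641 = 1.327
- e = 0.30: M = 0.9208/0.7924 = 1.162
- e = 0.50: M = 0.6947/0.7207 = 0.964

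For m = 0.7 (true rate ratio 0.50): P0 = 0.5630, P1 = 0.2687, Q = 0.1683, S = 0.4313.

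- e = 0.10: M = 0.5869/0.8832 = 0.665
- e = 0.30: M = 0.5006/0.8495 = 0.589
- e = 0.50: M = 0.4144/0.8158 = 0.508

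| True ratio | Extra exclusion, active | Extra exclusion, placebo | Per-protocol ratio |
|---|---|---|---|
| 1.00 | 30% | 10% | 1.162/1.327 = 0.88 |
| 1.00 | 50% | 10% | 0.964/1.327 = 0.73 |
| 1.00 | 10% | 30% | 1.327/1.162 = 1.14 |
| 1.00 | 10% | 50% | 1.327/0.964 = 1.38 |
| 1.00 | equal | equal | 1.00 |
| 0.50 | 10% | 10% | 0.665/1.327 = 0.50 |
| 0.50 | 30% | 30% | 0.589/1.162 = 0.51 |
| 0.50 | 50% | 50% | 0.508/0.964 = 0.53 |
| 0.50 | 10% | 50% | 0.665/0.964 = 0.69 |

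ITT recovers the true ratio in every row, provided that drop-outs are in fact followed.

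**4. Error rate and power.** A separate simulation used annual placebo rates of 0.5–1.0, dispersion 0.5, 24 months, 20 or 50 patients per arm, and a two-sided 0.05 test on the log rate ratio with empirical variance. These inputs are also assumed.

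- No true effect, 60% of patients with two or more relapses excluded on active and 20% on placebo: per-protocol ratio 0.74–0.76 and 12–23% rejection. ITT rejects in 5–6%.
- No true effect, 50% excluded in both arms: per-protocol ratio 0.99–1.01 and 6–7% rejection.
- True ratio 0.50, 60% excluded in both arms: estimate 0.50–0.55, and power falls from 36–88% (ITT) to 21–62%.
- True ratio 0.50, 90% excluded in both arms: only here does equal exclusion move the estimate clearly, to 0.62–0.65, with power 11–29%.

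**The case against.** The best defence is that this is a declared proof-of-concept study without a power calculation, in which per-protocol efficacy is an open choice. Investigators, patients and statisticians are blinded, drop-outs are followed, and ITT results will be produced and would expose a discrepancy. That lowers the risk. It does not remove it, because the trial has a formal success rule and ITT is only supportive.

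Some stronger readings are tempting, and the documents do not support them:

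- **That the paragraph takes three incompatible positions.** It takes two. The ITT label and the counting of relapses after discontinuation agree with each other.
- **That the protocol excludes patients who change therapy from the per-protocol set.** It calls them drop-outs. Their exclusion is an inference. The missing definition of a violation is not itself a fault, since it may stand in a statistical analysis plan.
- **That patients leave mainly because they relapse or cannot tolerate the oil.** The Note says only that the physician decides. Placebo is also an oil, every arm is made up to 19.5 ml with citrus aroma, and appearance and smell are to match.
- **That the bias favours the active arms.** Nothing fixes a direction. A false effect needs relapse-related exclusion to differ between arms, which blinding makes less likely. Unequal tolerability alone does not produce one: with tolerability exclusion of 30% against 10%, independent of an equal relapse-related exclusion, the per-protocol ratio stays at 1.00.
- **That the headline result is free to be picked after unblinding.** The last sentence does state an order. What stands is that *main* and *key* name different populations and the success rule names none.

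**Conclusion.** The concern holds as a contradiction in the protocol's own text and a poor choice of deciding population. It does not show that the result will be biased.

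Under the assumed inputs and no true effect, the per-protocol rate ratio can lie anywhere from about 0.73 to 1.38, against 1.00 for ITT. It returns to 1.00 when exclusion is equal in both arms. With a true ratio of 0.50, equal extra exclusion of 10–50% leaves the estimate at 0.50–0.53, so an effect is hidden mainly through lost power. Heavier exclusion on placebo (50% against 10%) dilutes it to 0.69.

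These figures rest on the assumed relapse rate, dispersion and exclusion shares, and on the inference that drop-outs leave the per-protocol set. The contradiction between the labels, and the silence of the success rule, rest on the text alone.

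**What to change.** Replace the last sentence of that Missing Data Handling paragraph with wording to this effect:

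> The key analysis of both endpoints is ITT: all randomised patients in their assigned arm, with all confirmed relapses and EDSS assessments over the planned analysis period, including those after discontinuation or change of therapy. The per-protocol analysis is supportive, and protocol violations are fixed before unblinding.

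Add to the success rule in Brief Statistical Methods that it refers to the ITT analysis. Use one label for the deciding analysis throughout.

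The cost is wording only, because follow-up of drop-outs is already required. The downside is some dilution of the effect by non-adherence, which the supportive per-protocol analysis can help to describe.

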Bottling of the interventions will be performed by a group of scientist (always by the same group of scientist) under the supervision of the involved specialist clinical biochemist at every six months. Interventions and placebo will have the same appearance and smell. The intervention will be bottled under the appropriate conditions, in dark bottle under Nitrogen bed; each coded patient will be assigned to a coded intervention or placebo according to the randomization scheme by HIONU. Both Intervention and placebo bottles will be packaged in a blank white carton box containing the dosage calibrated cup. Patients' codes and their representative intervention codes will be safely kept by HIONU. The independent safety/monitoring committee will be the only physical body that will have access on the safety codes; for use only at emergency and when absolutely necessary, when life threatening conditions such as severe site effects are unexpectedly introduced. The interventions will be handled and appropriately stored by the institution pharmacists. A new full bottle of the drug will be handled to a patient when the

previous bottle is empty returned. Pharmacists will keep a detailed record of intervention handling schedule to the patient.

The study is designed to end 30 months after enrolment and clinical assessments should be scheduled at entry baseline and at 3, 9, 15, 21 and 24 months on-treatment. An extra visit is required 6 months after the end of the study to confirm final EDSS score. Patients will be followed for an extended 12 month period with relapse recording. Patients will also be seen by the neurologist at unscheduled visits within 48 hours after the onset of new neurologic symptoms. If a relapse is suspected, the patient should be referred to the neurologist for evaluation and confirmation of any changes in the EDSS score.

Primary outcomes will be the **annual relapse rate** (**ARR**). **Relapses** are defined as new neurologic symptoms or worsening of pre-existing symptoms (that were stable for at least 1 month) not associated with fever or infection that lasts for at least 24 hours characterized by new or worsening neurological sign on examination as defined by previously described EDSS changes. The ARR for each treatment group is the mean of the annualized ARRs for all patients in the group calculated as the total number of confirmed relapses divided by the total number of days on study, multiplied by 365.25.

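### The protocol defines the group annualized relapse rate in two ways, which differ when follow-up varies, and does not say which gives the primary result

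*Protocol*

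**What the plan says.** The annualized relapse rate (ARR) is the primary outcome, and the protocol defines it twice.

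- **Study Procedures and End Points:** "The ARR for each treatment group is the mean of the annualized ARRs for all patients in the group". The sentence continues "calculated as the total number of confirmed relapses divided by the total number of days on study, multiplied by 365.25", without saying whether that ratio is formed per patient or per group.
- **Brief Statistical Methods, Primary Endpoint:** "The relapse rate will be calculated as the total number of relapses divided by the total number of patient-years followed for each treatment group". Differences in ARR are then to be "reported as percent difference (relative reduction").

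For inference the same section says "A Poisson regression/ negative Binomial analysis will be used to analyze this endpoint", with empirical standard errors and two-sided tests at 0.05.

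Two further points bear on the definition. Drop Outs and Missing Data Handling ask that patients who stop treatment be followed to the planned end. Missing Data Handling and Missing Data also provide for patients lost to follow-up, so some unequal follow-up is expected.

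**The concern.** A mean of patient rates gives a patient seen for a few months the same weight as one seen for two years. A pooled rate weights patients by time observed. These are different estimators, and the protocol does not rank them.

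Reading the second half of the first definition as a group total over a group total does not remove the conflict. It moves it inside one sentence, whose first half still asks for a mean over patients.

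At stake are the ARR reported for each arm and the percent reduction, which is likely to be the headline result. With both definitions in force, the choice could be made after the data are seen. The trial is exposed to this because enrolment is limited to the eligible patients of one country, split over four arms, so one early loss can move an arm's figure.

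**Working it through.** The protocol states no sample size, expected ARR or loss rate, so there is no planned figure to reproduce. All numbers of patients, relapses and losses below are assumptions. Only the formulas and the 24-month period after entry baseline come from the protocol.

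**Formulas.** Let patient i have r_i relapses in t_i years, with n patients in the arm.

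- A, mean of patient rates: (1/n) × Σ(r_i / t_i)
- B, pooled rate: Σr_i / Σt_i

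**One arm of 10 patients, 24 months planned**

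| Case | A | B |
|---|---|---|
| 12 relapses, all followed 2 years | (12/2)/10 = 0.600 | 12/20 = 0.600 |
| Same 12 relapses, one patient with 1 relapse lost at 3 months | (11/2 + 1/0.25)/10 = 0.950 | 12/18.25 = 0.658 |
| 11 relapses, the patient lost at 3 months had none | (11/2)/10 = 0.550 | 11/18.25 = 0.603 |

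The formulas agree with equal follow-up, and the gap can go either way without it.

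**Which one the model estimates.** An intercept-only Poisson regression with log(t_i) as offset, fitted to the second row, returns 0.658. That is B, not A. A negative binomial fit solves μ = Σw_i r_i / Σw_i t_i with w_i = 1/(1 + kμt_i), where k is the dispersion. It equals B at k = 0 and moves towards A as k grows: with k fixed at 1 the second row gives 0.705. It still weights by follow-up time and is not the simple mean of rates.

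**Two arms of 20, effect on the percent reduction**

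- Placebo: 24 relapses, all followed 2 years. A = (24/2)/20 = 0.600; B = 24/40 = 0.600.
- Active: 10 relapses. Ten patients have none and nine have one, all with 2 years of follow-up. One has one relapse and is lost at 3 months. A = (9 × 0.5 + 1/0.25)/20 = 0.425; B = 10/(38 + 0.25) = 0.261.
- Reduction under A: 1 − 0.425/0.600 = 29.2%. Under B: 1 − 0.261/0.600 = 56.4%.

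The time of loss drives the size. Putting t for 0.25 in the active arm gives:

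| Lost at | A | B | Reduction A | Reduction B |
|---|---|---|---|---|
| 3 months | 0.425 | 0.261 | 29% | 56% |
| 6 months | 0.325 | 0.260 | 46% | 57% |
| 12 months | 0.275 | 0.256 | 54% | 57% |
| 24 months (no loss) | 0.250 | 0.250 | 58% | 58% |

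**Typical size by simulation.** Assumed: 20 per arm, true ARR 0.8 against 0.4, gamma frailty with dispersion 1, time of loss uniform from 0.1 to 2 years, 4,000 replicates. The table gives the absolute gap between the two percent reductions. The first value in each range is for loss unrelated to relapse risk, the second for loss related to it.

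| Share lost | Median gap (points) | 95th percentile (points) |
|---|---|---|
| 0% | 0 | 0 |
| 10% | 2 to 4 | 15 to 22 |
| 20% | 4 to 6 | 23 to 30 |
| 40% | 6 to 9 | 31 to 44 |

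**The case against.** **The test does not depend on it.** Success is defined by a significant difference, and the regression supplies that test. A reader might infer that the primary p-value turns on which formula is used. The text does not support this: both formulas describe the group rate and the percent reduction, and the p-value need not change. This point stands and limits the finding to what is reported.

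**Follow-up may be nearly complete.** Drop-outs are to be followed to the end. If that succeeds, the formulas nearly coincide. This stands too, but the protocol itself expects losses. Its last-observation-carried-forward rule does not say that a lost patient's follow-up time is extended, so it does not settle the choice.

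**The statistical section is clear.** One can treat the pooled formula as governing and the other sentence as loose wording. That is a sensible reading, but the protocol does not state it.

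**The pooled rate is not better in every respect.** In the simulation with 20% lost and loss related to relapse risk, the mean of rates stayed near the true placebo ARR (0.799) while the pooled rate fell to 0.734. In the active arm the figures were 0.400 and 0.364. The ratio was hardly affected (0.364/0.734 = 0.50).

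**Two stronger readings should not be drawn.**

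- A reader might infer that every ARR is understated by 20%, from 1 − 24/30, because "The actual research period is for a total of 30 months including 6 months normalization and 24 months treatment periods". No section tells the analyst to divide relapses from months 6 to 30 by 30 months. Days on study is undefined, and a factor common to all arms would cancel in the percent reduction.
- A reader might infer a fixed loss of precision from averaging patient rates. Its size depends on when patients leave, which the protocol does not give, so no figure is warranted.

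**Conclusion.** The inconsistency is real and concerns the definition of the primary endpoint. The protocol gives an equally weighted mean of patient rates in one place and a rate pooled over follow-up time in another, and does not say which yields the primary ARR and percent reduction. The planned model goes with follow-up-time weighting: exactly with the pooled rate for a Poisson fit without covariates, and approximately otherwise.

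The size depends on early losses. In the illustration a single relapsing patient lost at 3 months separates the reductions as 29% and 56%. If the loss comes at 12 months they are 54% and 57%, and with complete follow-up there is no difference. These figures rest on an assumed 20 patients per arm and assumed relapse counts. The conclusion covers the reported rates and percent reduction, not the significance test.

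**What to change.** Use one definition in both Study Procedures and End Points and Brief Statistical Methods:

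- **Primary ARR:** confirmed relapses divided by patient-years observed, per arm. Use the word confirmed in both places, since the statistical formula now omits it.
- **Window:** count relapses and follow-up time over the same stated period. The Note on the normalization period and the definition of the on-treatment period point to the 24 months after entry baseline. The undefined days on study should be replaced accordingly.
- **Effect measure:** take the rate ratio and its 95% confidence interval from the regression, with log follow-up time as offset, and report the percent reduction as 100 × (1 − rate ratio).
- **Mean of patient rates:** delete it or label it descriptive only.

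The cost is an edit of a few sentences. It needs no new data and no change to the planned test. If losses prove related to relapse risk, the pooled arm-level rates can be somewhat low, and showing the mean of patient rates as a labelled descriptive figure would make that visible.
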